Long-term outcomes of successful chronic total occlusion percutaneous coronary interventions using the antegrade and retrograde dissection and re-entry approach.

(LOTUS-ADR/RDR)

Protocol

Sponsored by: Department of Cardiology, Xi'jing Hospital.

The Fourth Military Medical University (FMMU)

Approved by: Ethics Committee, Xi'jing Hospital. FMMU

Approved Ethical Number: KY20172019-1

Approved date: 2017.03.15

Last Update: 2018.11.20

Study Time: 2018.12.01- 2019.12.30

Versions: V2.0

ABSTRACT

BACKGROUND: Chronic total occlusion (CTO) angioplasty is one of the most challenging procedures remaining for the interventional operator. Today, with contemporary CTO negotiation available strategies and significant operator expertise, the literature reports a 50-95% success rate for recanalizing CTOs. But PCIs of CTO lesions still carry a high rate of in-stent restenosis (ISR). Because previous reports have not specifically compare contemporary antegrade and retrograde dissection and re-entry dissection (ADR/RDR) technique on the long-term impact of ISR, so the investigators focused on the objective.

OBJECTIVES: This study hope to evaluate the frequency of angiographic ISR and further elucidate some ISR related higher risk factors among CTO PCI patients in intimal stent group using antegrade or retrograde wire escalation (AWE/RWE) techniques and sub-intimal stent group using contemporary antegrade or retrograde dissection and re-entry (ADR and/or RDR).

METHODS: A total of 300 consecutive selected patients with CTO lesion who will undergo successful revascularization by AWE/RWE and ADR/RDR techniques treatment will be enrolled in this prospective multicenter registry from December 1 2018 to December 31 2019. The primary study endpoint of the protocol is the binary in-stent restenosis of CTO vessels at angiographic follow-up about 13 months. The secondary endpoints are: 1) CTO technique and procedure success rate; and 2) in-hospital and 30 days MACE (Cardiac death, acute myocardial infarction, urgent repeat target vessel revascularization with either pericardiocentesis or surgery and stroke and stent thrombosis and stroke); 6months and 1-year and 2-year MACE including death, MI, and target CTO vessel revascularization and stroke ; and 3) Restenosis scores (R-scores) of related risk factors.

CONCLUSIONS: This study expect to identify long-term effect of ADR and RDR methods on the ISR incidence and predictors.

INTRODUCTION

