be a direct consequence of subintimal stenting. If the cause of the high incidence of restenosis is, in fact, due to use of the subintimal space, newer CTO techniques, which are based on controlled subintimal dissection and reentry methods, also would be expected to be associated with this adverse outcome²⁵⁻²⁸ Now there are only limited data about procedural success of ADR and RDR and retrograde techniques have been demonstrated and the use of subintimal stenting did not adversely impact outcomes^{34, 35}. While prospective studies with longer follow-up are needed to assess the long-term safety and efficacy of sub-intimal stenting.

The purpose of the study was therefore to examine the longer-term outcomes of patient who underwent successful CTO PCI in our program, compare the effect of ADR/RDR on outcomes with everolimus-eluting stents (EES) and assess predictors of long-term events.

METHODS

1. Trial overview and study population.

① This clinical trial is a prospective, exploratory, nonrandomized, multicenter trial evaluating the frequency of angiographic restenosis and clinical outcomes among patients undergoing CTO PCI in intimal stent group using antegrade or retrograde wire escalation (AWE/RWE) techniques and sub-intimal stent group using contemporary antegrade or retrograde dissection and re-entry (ADR or RDR) with everolimus-eluting stents (XIENCE Coronary Stent).

② According to high patient's volume registry studies in CTO lesions, the patients percentage of ADR or RDR strategy application was just only 20-25%³⁶⁻³⁷. If to get 60 patients for ADR or RDR strategies, the minimum CTO number are 300 patients. So in our registry study, 300 CTO cases, to which PCI will be attempted, are prospectively enrolled from December 1 2018 to December 31 2019 in the CTO registries of ten centers. The study was approved by the institutional review board at each site. For patients with multiple treated CTO, only the first CTO attempted was considered for the analysis.

③ Exclusions included age <18-years-old or >85-years-old, left ventricular ejection

fraction $\leq 30\%$, allergy to medications (antiplatelet drugs, heparin, metal alloys, or contrast agents), a planned surgery within 6 months of PCI or planned thrombolysis, pregnant, a life expectancy of <6 months.

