Discrete data are summarized as frequencies and continuous data as mean \pm SD or median and interquartile range. Chi-square test or Fisher exact test analyses were used for comparison of categorical variables. The multivariable analysis to evaluate the independent contribution of clinical, angiographic, and procedural variables to re-occlusion and in-segment restenosis was performed by forward stepwise logistic regression analysis. Cumulative survival analyses were performed using the Kaplan-Meier method, and the difference between curves was assessed by log-rank test. A multivariable analysis by forward stepwise Cox proportional hazards model was performed to evaluate the independent predictors of death, myocardial infarction, and target CTO vessel revascularization. Odds ratios (ORs), hazards ratios (HRs), and their 95% confidence intervals (CIs) were calculated.

All tests were 2-tailed. A p value <0.05 was considered significant. Analyses

were performed using the software package SPSS (version 11.5, SPSS Inc., Chicago, Illinois).

REFERENCE

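### The plan expects to identify the effect of ADR/RDR on restenosis predictors, but specifies no analysis that could show whether predictors differ by technique

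*Combined protocol and SAP*

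**What the plan says.** The aim appears in three places, worded differently.

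- Abstract, Conclusions: "This study expect to identify long-term effect of ADR and RDR methods on the ISR incidence and predictors".
- Abstract, Objectives: the study is to "further elucidate some ISR related higher risk factors among CTO PCI patients in intimal stent group using antegrade or retrograde wire escalation" techniques; the sentence then goes on to the sub-intimal group.
- End of the Introduction: the purpose is to "compare the effect of ADR/RDR on outcomes with everolimus-eluting stents (EES) and assess predictors of long-term events", with nothing specific to a group.

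Methods item 1 calls the study a "prospective, exploratory, nonrandomized, multicenter trial". On numbers it says "the patients percentage of ADR or RDR strategy application was just only 20-25"% in earlier registries, and then "If to get 60 patients for ADR or RDR strategies, the minimum CTO number are 300 patients".

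Methods item 4 covers predictors of restenosis in one sentence: "The multivariable analysis to evaluate the independent contribution of clinical, angiographic, and procedural variables to re-occlusion and in-segment restenosis was performed by forward stepwise" selection in a logistic model. The other tools listed are chi-square or Fisher tests, Kaplan-Meier curves with a log-rank test, and a forward stepwise Cox model for clinical events. There is no candidate list, interaction term, model by group, or rule that technique stays in the model.

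**The concern.** Whether a technique affects the predictors of an outcome is a question of effect modification. It needs an estimate of each predictor's effect in each technique group, or of the difference between them. A model with a single odds ratio per predictor gives neither, and forward selection may also remove technique itself.

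Equal effects in the two groups cannot be taken for granted. The Introduction asks whether subintimal stenting itself causes restenosis. Methods item 3 makes wire escalation the first choice, so many ADR/RDR patients would be those in whom it failed. One of the R-score factors, dissection length, is tied to the dissection techniques.

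Two errors could follow. A predictor that matters only for subintimal stents could be diluted and missed, and one that acts only in wire-escalation patients could be reported as applying to subintimal stents.

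**Working it through.** **1. The plan's own figure.** N = target number / expected share. 60/0.20 = 300, which matches; 60/0.25 = 240. So 300 uses the lower end of 20-25%. It is a recruitment count, not a power calculation. A share of 25% would give 0.25 × 300 = 75. The splits to examine are therefore 60 ADR/RDR v 240 wire, and 75 v 225.

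**2. Aims against analyses.** Let T be technique and X a predictor, with logit P(restenosis) = a + bT + dX + gTX.

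- Incidence by technique: served, unadjusted, by the chi-square or Fisher test.
- Predictors across the combined cohort (d): served by the stepwise logistic model.
- Whether predictors differ by technique (g, or d estimated by group): nothing is specified.

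**3. Which group drives a common odds ratio.** The documents give no restenosis rates, so the rates below are assumptions. ADR/RDR share of events = n₂p₂/(n₁p₁ + n₂p₂). Share of logistic information replaces p with p(1−p).

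| Rate, wire v ADR/RDR | Events, 60/240 | Information, 60/240 | Events, 75/225 | Information, 75/225 |
|---|---|---|---|---|
| 10% v 10% | 6/30 = 20% | 20% | 25% | 25% |
| 10% v 20% | 12/36 = 33% | 31% | 40% | 37% |
| 10% v 30% | 18/42 = 43% | 37% | 50% | 44% |
| 5% v 25% | 15/27 = 56% | 50% | 62% | 57% |

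ADR/RDR reaches half of the events at a rate ratio of 240/60 = 4 or 225/75 = 3. By information the threshold is somewhat higher: with wire at 5%, ADR/RDR needs 25.5% (60/240) or 17.2% (75/225). With wire at 10%, no ADR/RDR rate gets there.

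**4. What a common odds ratio would report.** Simulated trials with 240 and 60 patients, and a logistic model with technique and one standardised predictor; odds ratios are per SD.

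| Rate, wire v ADR/RDR | OR 1.0 wire, 2.5 subintimal: pooled OR (p<0.05) | OR 2.0 wire, 1.0 subintimal: pooled OR (p<0.05) |
|---|---|---|
| 10% v 10% to 10% v 30% | 1.17-1.35 (13-39%) | 1.55-1.73 (66-79%) |
| 15% v 25% | 1.26 (32%) | 1.68 (92%) |
| 5% v 25% | 1.50 (46%) | 1.46 (45%) |

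Results move a little with the simulation run and with whether the rate is set overall or at the predictor's average value. The latter gives 1.22 and 1.77 at 10% v 10%. Rounded, the ranges are 1.2-1.5 and 1.5-1.8.

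The weight given to the subintimal group follows on the log scale. At 15% v 25% it is ln 1.26/ln 2.5 = 0.25, and from the other scenario 1 − ln 1.68/ln 2.0 = 0.25. At 5% v 25% it is ln 1.50/ln 2.5 = 0.44 and 1 − ln 1.46/ln 2.0 = 0.45. The lean toward wire escalation has then nearly gone, but the common odds ratio describes neither group.

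**5. What a by-group analysis could deliver.** The SE of the subintimal log OR per SD is about 0.3-0.5. Since exp(1.96 × 0.3) = 1.8 and exp(1.96 × 0.5) = 2.7, the 95% CI runs from the estimate divided by 1.8-2.7 to the estimate multiplied by the same factor. Interaction power is about 27-67% for the all-or-nothing effects in step 4. At 15% v 25% it is 22% for OR 1.5 v 2.5 and 13% for 2.0 v 1.5. For a binary predictor of 50% prevalence, OR 1 v 3 and rates of 10% v 10-30%, it is 18-35%, or 15-29% if 80% have angiography. A full model in 60 ADR/RDR patients at 10-30% restenosis would have 6-18 events, or 1-3 per R-score factor, so that is not the remedy.

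**The case against.** The strongest reply is that the plan promises less than it seems to. The objective can describe one cohort made up of both stent groups, and the Introduction speaks only of assessing predictors. No listed endpoint is a technique-by-predictor contrast. Even the Conclusions sentence could be read as the effect on incidence, plus the predictors of restenosis. This stands in part: a reader might infer a firm promise of separate risk factors in each stent group, and the text is too loose for that. The Conclusions sentence is the better anchor. On its plain wording it links technique to predictors, and no analysis is specified for that link.

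A reader might also infer that the plan prescribes a pooled main-effects model. It does not say so. It neither states nor excludes interactions or group fits, so the supportable statement is that none is specified.

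The simulated effects are all-or-nothing, and technique is forced in rather than selected stepwise, so they illustrate the mechanism and do not forecast results. Where effects are alike in both groups, pooling does no harm and is more precise.

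Finally, low-power interaction tests may reasonably be left out of an exploratory study. That is fair for tests, but a claim about predictors by technique still needs an estimate behind it, or should be withdrawn.

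**Conclusion.** The point holds as a gap between a stated aim and the specified analysis: nothing in Methods item 4 can show whether predictors of restenosis differ by technique. That conclusion needs no assumed rate.

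The size does. A reader might infer that the reported predictors will mostly be those of the wire-escalation patients. This is certain only for the planned patient counts (225-240 of 300, or 75-80%). For events it fails once ADR/RDR restenosis is about three to four times higher or more, which cannot be dismissed given the Introduction's own worry about subintimal stenting. Under the assumed rates and a 60/240 split, one-sided effects pool to about 1.2-1.5 (true OR 2.5, subintimal only) or 1.5-1.8 (true OR 2.0, wire only).

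The number of ADR/RDR patients with the endpoint may also fall below 60. The Abstract counts 300 successful cases, Methods item 1 counts 300 attempted ones, and patients with moderate or severe renal insufficiency are not scheduled for the 13-month angiogram.

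**What to change.** Either of two changes closes the gap.

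- **Add the analysis.** Keep technique in the restenosis model regardless of its p value. Pre-specify at most three predictors measurable in both groups, for example total stent length, final lumen area and calcification. For each, report the odds ratio with 95% CI in each group and the interaction estimate, without selection by p value, and label the results exploratory.
- **Narrow the claim.** Limit the objective and conclusion to predictors across the combined cohort, and drop the statement about the effect of ADR/RDR on predictors.

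The first costs up to three model terms on data already to be collected; the second costs a few reworded sentences. Neither changes treatment, visits or recruitment. The downside of the first is imprecision: an SE of about 0.3-0.5 per SD for the subintimal log OR, more with several predictors or incomplete angiography. A non-significant interaction must not be read as evidence that predictors are the same.

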For the main analysis, the investigators consider that the lesion is crossed with dissection/re-entry when (1) a wire-based antegrade dissection was performed followed by re-entry into the true distal lumen with a straight or knuckled wire/CrossBoss, (2) A Stingray system was used to cross from the false lumen to the true lumen, and (3) when a reverse-controlled antegrade and retrograde re-entry technique is used to cross the CTO segment. Other CTO crossing techniques were considered “intraplaque,” “true-to-true,” or wire escalation techniques(as **figure 1**).

3. Intervention Procedures

- ① All patients receive optimal intravenous hydration the days before and after PCI.
- ② Patients receive an initial bolus of intravenous unfractionated heparin (100 IU/kg). The activated clotting time is monitored every 30 min to determine if an additional bolus of unfractionated heparin is necessary to maintain an activated clotting time >250s. Upstream use of glycoprotein IIb/IIIa inhibitor therapy or bivalirudin is avoided.
- ③ All procedures are performed via the radial or/and femoral route, with double coronary cannulation and contralateral selective injection. Seven-French guiding catheters are used in most cases.
- ④ All operators have received proctoring in AWE, antegrade dissection re-entry (ADR), retrograde wire escalation (RWE) and retrograde dissection re-entry (RDR) approaches used in the hybrid algorithm. And operators have performed a career minimum of 300 CTO cases.
- ⑤ To adjust the patients number in intimal stents group and subintimal stents group with either the antegrade or the retrograde approach, wire escalation technique was made as the first choice in all patients, if failed, to choose which CTO revascularization strategy is left to the operator’s discretion (Fig 1). The selection of the optimal initial CTO crossing strategy is dependent on the anatomy of the coronary vessels. Four angiographic characteristics are used to make the decision (Fig. 1): (a) lesion length (lesions ≥ 20 mm in length tend to have lower success rates and longer procedure times using standard antegrade wire escalation); (b) proximal cap location and morphology; (c) size, quality (i.e. vessel size and presence of luminal stenoses

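### The comparison of ADR/RDR with wire escalation on 13-month restenosis has no planned analysis that is sure to give an adjusted group estimate

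*Combined protocol and SAP*

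**What the plan says.** **A comparison is stated.** The Abstract gives the lack of earlier reports comparing ADR/RDR on long-term restenosis as the reason for the study. The Introduction sets out to "compare the effect of ADR/RDR on outcomes with everolimus-eluting stents (EES", alongside a search for predictors. Methods 1, item 2 sizes the registry to yield 60 ADR/RDR patients. The last paragraph of Methods 2 defines the exposure: "For the main analysis, the investigators consider that the lesion is crossed with dissection/re-entry when" one of three crossing routes was used. All other techniques form the comparison group.

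**Technique depends on the lesion.** Methods 1 calls the trial exploratory and nonrandomised. In Methods 3, item 5, "wire escalation technique was made as the first choice in all patients, if failed", the next strategy is left to the operator. The same item adds "Four angiographic characteristics are used to make the decision": lesion length, proximal cap, distal vessel with its side branches, and collaterals. Methods 2, items 8 and 9 also tie the approach to lesion length, cap clarity and distal target.

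**The analysis plan.** Methods 4 says "Chi-square test or Fisher exact test analyses were used for comparison of categorical variables" and, for survival curves, "the difference between curves was assessed by log-rank test". It has only two multivariable analyses. In the first, the assessment of what each candidate variable contributes "to re-occlusion and in-segment restenosis was performed by forward stepwise logistic regression analysis". The second is a forward stepwise Cox model for clinical events. Candidates are described only as clinical, angiographic and procedural variables. No entry or removal criteria are given, no term is forced in, and no propensity score, matching, weighting or stratification is planned.

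**The concern.** The Introduction names calcification, CTO length and diabetes as restenosis predictors. Length is therefore both a reason for choosing a technique and a cause of the outcome. A raw difference in restenosis may show which lesions went to ADR/RDR rather than what subintimal stenting does.

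The direction cannot be presumed. Methods 2, item 9 prefers device-based ADR for longer lesions, which would make ADR/RDR look worse. It also asks for a good distal re-entry zone, which would make it look better. A spurious difference and a hidden real one are both possible.

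The stepwise models serve the predictor search, which is a separate stated aim. For the group comparison they may report no technique estimate, or one with lesion confounders left out.

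**Working it through.** **1. The plan's own figure.** 60 / 0.20 = 300, as stated in Methods 1, item 2. (At the 25% share it would be 60 / 0.25 = 240.) The working split is therefore 60 versus 240. The documents give no restenosis rate, effect size or lesion imbalance, so every input from step 3 on is assumed.

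**2. What each planned analysis guarantees.**

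| Planned analysis | Group kept? | Lesion factors kept? |
|---|---|---|
| Chi-square / Fisher | yes | no |
| Log-rank | yes | no |
| Stepwise logistic | only if selected | only if selected |
| Stepwise Cox | only if selected | only if selected |

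No row has both. This result rests on the text alone.

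**3. Crude bias by hand.** Take independent binary features, each with odds ratio θ for restenosis and prevalence p1 (ADR/RDR) and p0 (wire escalation). Then approximately

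crude OR ≈ true OR × product of [1 + (θ−1)p1] / [1 + (θ−1)p0].

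- Moderate, no true effect (two features, θ = 2, 70% vs 45%): (1.70/1.45)² = 1.37.
- Weak, no true effect (two features, θ = 1.5, 60% vs 45%): (1.30/1.225)² = 1.13.
- Opposite direction, true OR 2 (distal disease, θ = 2, 30% vs 50%): 2 × 1.30/1.50 = 1.73.

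**4. Simulation** at 60 versus 240, with 10% and 20% restenosis under wire escalation. The adjusted model is group plus a propensity score from ten items: five J-CTO items, proximal cap location, distal disease, cap side branches, collaterals and diabetes.

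| Case | Crude OR | Chi-square rejects | Adjusted OR | Adjusted rejects |
|---|---|---|---|---|
| Moderate, null | 1.3-1.4 | 11-18% | 0.94-1.00 | 4-6% |
| Weak, null | 1.10-1.14 | 6-7% | – | – |
| Opposite, true OR 2 | 1.67-1.72 | – | 1.94-2.01 | – |

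These runs are a best case, because every confounder is measured.

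**5. The J-CTO items alone are not enough.** Suppose distal disease is the confounder at the null (OR 3, 50% vs 20%; by hand 2.0/1.4 = 1.43). A score from J-CTO items and diabetes leaves OR 1.39-1.45 and 13-19% rejection. The ten-item score gives 1.01-1.02 and 4-5%.

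**6. Unmeasured selection.** Add to the moderate null case one uncoded feature (θ = 2, 70% vs 20%). By hand it contributes 1.70/1.20 = 1.42, so the crude OR is 1.3745 × 1.4167 = 1.95 and about 1.42 remains after adjustment. Simulation gives a crude OR of about 1.9 with 38-53% rejection, and an adjusted OR of about 1.4 with 13-16%. A milder feature (θ = 1.5, 60% vs 30%) leaves an adjusted OR of 1.13-1.15 with 6-7% rejection, against 1.54-1.59 and 21-28% crude.

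**7. Stepwise** (11 candidates; entry p<0.05 and removal p>0.10 assumed). At the null, group is kept in 6-7% of runs, against 4-5% rejection by the forced model. With true OR 2, group is absent in 38-56% of runs, but the forced model is itself non-significant in 46-68%. When group is kept, at least one true lesion confounder is missing in 68-95%.

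**8. Events.** 300 × 10% = 30 and 300 × 20% = 60. Group plus ten separate covariates is 11 terms, or 30/11 = 2.7 to 60/11 = 5.5 events per term. Group plus one score is two terms, or 15 to 30.

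**The case against.** The strongest reply is that the plan already adjusts. Methods 3, item 6 records the crossing approach, so technique can be a procedural candidate beside the angiographic ones. The study is labelled exploratory, and the Abstract's objective is restenosis frequency and risk factors, for which stepwise selection is not at issue. This stands in part: adjustment is possible, and the exploratory label lowers the severity. But adjustment is not assured, and the Introduction and Methods 2 do state a group comparison.

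A second reply is that the stepwise evidence is modest. This also stands. The excess retention at the null is small, and much of the dropping reflects low power that a forced model shares. A reader might infer that the stepwise estimate has been shown to be biased by a known amount. It has not: missing confounders are expected when selection runs on few events, and no bias figure is offered here. The larger numerical distortions come from the unadjusted tests.

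Third, adjusting for coded factors cannot make the groups comparable. Failed wire escalation largely defines the ADR/RDR group. Vessel size guides the choice in Methods 3, item 5 but is not coded in Methods 2, item 6. Operator discretion operates across ten centres. Step 6 shows that this objection is right about what remains, but also that the crude comparison is worse.

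**Conclusion.** The point holds as a gap in the plan: a stated, nonrandomised comparison has no analysis that is sure to give an adjusted group estimate. Confidence in that reading is high, because it rests on the text.

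Confidence in the size is much lower. Under assumed inputs the harm ranges from slight (about 6% rejection) to moderate (11-18%), and a true OR of 2 can shrink to about 1.7. The near-nominal behaviour of the adjusted model assumes that all confounders are measured.

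A reader might infer that the proposed model would yield an unbiased technique effect, or that the plan's comparison must be biased against ADR/RDR. The documents support neither. Important selection factors are uncoded, and the stated selection rules push in both directions. This is a cheap improvement to an exploratory study and does not invalidate it.

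**What to change.** - **Main comparison.** Prespecify one logistic model for 13-month restenosis with group (ADR/RDR vs AWE/RWE) always kept. Adjust for the pre-crossing factors coded in Methods 2, items 5 and 6: the five J-CTO items, proximal cap location, distal-vessel disease, cap side branches and interventional collaterals, plus diabetes if recorded.
- **Form.** A propensity score as a single covariate suits the few events. A short fixed covariate list or weighting is an acceptable alternative.
- **Timing of readings.** Methods 2, item 6 allows length and tortuosity to be read after crossing or equipment passage. Use pre-crossing readings where available, and flag patients who have only later ones.
- **Leave out** stent number, stent length, dissection length and final lumen area (Methods 3, item 8). They arise during or after crossing and may carry part of the technique effect.
- **Other analyses.** Use the same forced-group structure in the Cox model. Label the chi-square and log-rank group comparisons descriptive. Keep stepwise selection for the predictor search.
- **Limitations to state.** Failed wire escalation, uncoded vessel size, and centre and operator preference remain sources of confounding. Centre may be examined in a sensitivity analysis.

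**Cost.** Wording in Methods 4 and a note on reading times; every adjustment item except diabetes is already coded. The standard error is roughly 3-14% larger than for the crude comparison. Power stays low: for a true OR of 2 at 60 versus 240, about 43-59% for the unadjusted comparison and 32-56% with the score.
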